8. Community rates of COVID based on 7 day moving average.

Power/Sample Size

Personal Contacts (12-14 month & 4-year-olds) Trial:

We based our hypotheses (see table, below) on a systematic review's pooled estimates of effect size for automated messages and personalized calls finding 37% and 40% of children, respectively, completed immunizations.¹ Because of the significant cost involved in making personal contacts, the minimal difference in outcome that would make it worth the effort is high.

Hypotheses	% of children who receive MMR by 15 months of age	
	1 automated message sent	2 automated messages sent
0 personal attempts	20% ^C	35% ^B
1 personal attempt	50% ^A	65% ^{AB}

We calculated sample size needed per group to detect a difference for each of the contrasts below with alpha of 0.05 and power of 80%.

Contrast	Sample Size per Group
A vs C	36
B vs C	136
A vs. B	167
A vs. AB	167
B vs. AB	40
C vs. AB	16

To fully power the 2 X 2 factorial trial, we estimate needing 167 per group X 4 groups = 668 total subjects. There are currently 712 children eligible for the study. More will become eligible every month so we expect to far exceed the required sample size after 3 replications. If needed, we could increase the number of replications of the trial to reach the targeted sample size. We acknowledge that we are not powered to precisely estimate any interactions between interventions.

MyChart Trial:

In hypothesis testing for 0 message vs. 1 message vs. 2 messages, we will do the testing in a fixed sequence - test 2 messages vs. 0 message first, only if it is significant then test 2 messages vs. 1 message, thus the type I error rate of 0.05 is retained. Since the hypothesis testing of 2 messages vs. 0 message would be considered easier to achieve than the hypothesis testing of 2 messages vs. 1 message, the power analysis for this trial should be based on the design of (standard message vs. tailored message) by (1 message vs. 2 messages). We based our hypotheses (see table, below) on previous work indicating approximately 20% WCC appointment completion on automated text reminders. We anticipate that a tailored message increases the WCC appointment completion rate by another 10%.

Hypotheses		% of children complete WCC within 8 weeks

	No message	1 automated message sent	2 automated messages sent
Standard Message	2%	10% ^C	20% ^B
Tailored Message		20% ^A	30% ^{AB}

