We calculated sample size needed per group to detect a difference for each of the contrasts below with alpha of 0.05 and power of 80%.

Contrast	Sample Size per Group
A vs C	199
B vs C	199
A vs. AB	293
B vs. AB	293
C vs. AB	62

We assume no difference between A vs. B and thus not consider powering the comparison between these two groups, but we will explore non-inferiority analysis for this comparison in data analysis. To fully power the above contrasts, we estimate needing 293 per group X 4 groups = 1172 subjects. Adding 293 in the zero message group, we would need a total of 1465 subjects. There are currently 1000 children eligible for the study. More will become eligible every month so we expect to exceed the required sample size after 2 replications. If needed, we could increase the number of replications of this trial to reach the targeted sample size. We acknowledge that we are not powered to precisely estimate any interactions between interventions.

Televox (6-11yo) Trial:

We calculated sample size based on the following hypotheses:

% of children complete WCC within 8 weeks		
no message	2 Low Tailored Messages	2 High Tailored Messages
2%	20%	30%

With alpha of 0.05 and power of 80%, to fully power the contrasts between the above groups, we need 293 per group X 3 groups=879 subjects. Currently there are 2500 kids eligible, so we expect to reach the targeted sample size.

Televox (12-17yo) Trial:

We calculated sample size based on the following hypotheses:

% of children complete WCC within 8 weeks		
no message	2 Low Tailored Messages	2 COVID Tailored Messages
2%	30%	40%

With alpha of 0.05 and power of 80%, to fully power the contrasts between the above groups, we need 356 per group X 3 groups=1068 subjects. Currently there are 1100 kids eligible, so we expect to reach the targeted sample size.

Analysis

We will conduct descriptive analyses to characterize the participants in terms of demographics and other potential covariates in consideration (child age group, parent's preference for call vs. text mode of contact, whether parent

Outreach Methods Study Protocol & SAP

Version 1.1, 1/14/22

pg. 9

had activated MyChart account, access to appointment, whether patient receipt of any past immunizations, historic no show rate, and community rates of COVID). We will use chi square tests to examine whether participants in the 4 groups are similar in these characteristics.

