For the Personal Contact (12-14 mo & 4 years old) trials, we will conduct intent-to-treat analyses using logistic regression models (without adjusting for covariates) for each of our three binary outcomes: completed appointment within 2 weeks, completed appointment within 8 weeks, receipt of MMR by 15 months of age or receipt of 2nd MMR by 3 months after randomization. We will do pair-wise comparison among the 4 groups and adjust p value of each comparison for multiplicity. If participants in the 4 groups differ on potential covariates, we will conduct additional analyses adjusted for these variables.

For the MyChart and Televox Trials (6-17 years old), we will conduct intent-to-treat analyses using logistic regression models (without adjusting for covariates) for each of the binary outcomes: scheduled appointment within 2 weeks, completed appointment within 8 weeks, receipt of 1st dose of COVID vaccination (age 12-17 years) within 8 weeks, family member receipt of COVID vaccination within 8 weeks. We will do pair-wise comparison among the treatment groups and adjust p value of each comparison for multiplicity. If participants differ in potential covariates across treatment groups, we will conduct additional analyses adjusted for these variables. We will explore non-inferiority analysis for comparison the two groups that are expected to have similar appointment scheduled and completion rate in the MyChart trial.

We will also conduct per-protocol analyses according to the interventions actually received by the participants, recognizing that actual intervention received could be different from initial randomized intervention. For example, a parent allocated to group A might schedule an appointment after receiving the automated message and therefore would not receive a personalized contact attempt. In addition, we may explore potential interaction between the two interventions as a secondary analysis. All analysis will be conducted using SAS version 9.4.

Duration

The study will begin upon IRB approval and continue through December 31, 2022. During this time, we will discuss the significance of data, potential future projects and dissemination of results.

Process of Obtaining Consent

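### The 80% power is for contrasts tested at an unadjusted 0.05, but the analysis adjusts the pairwise p values by an unnamed method, leaving the size-setting Personal Contacts and MyChart contrasts below 80% at the minimum sizes

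*Combined protocol and SAP*

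**What the plan says.** **Sizing.** Protocol, Power/Sample Size, sets the Personal Contacts and MyChart group sizes to "detect a difference for each of the contrasts below with alpha of 0.05 and power of 80" per cent, and takes the largest result in each trial. For Personal Contacts: "To fully power the 2 X 2 factorial trial, we estimate needing 167 per group X 4 groups = 668 total subjects". For MyChart: "To fully power the above contrasts, we estimate needing 293 per group X 4 groups = 1172 subjects", to which a no-message group of 293 is added (1465 in total). The Televox trials are sized at the same alpha and power, at 293 per group (6-11 years) and 356 per group (12-17 years).

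These sizes are minimums. For Personal Contacts the protocol adds "There are currently 712 children eligible for the study" and "we expect to far exceed the required sample size after 3 replications". It also expects to exceed the MyChart target, and allows further replications in both trials.

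**Analysis.** Protocol, Analysis, plans "We will do pair-wise comparison among the 4 groups and adjust p value of each comparison for multiplicity" for Personal Contacts, and an equivalent sentence covers MyChart and Televox. No method is named in the protocol or the SAP.

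**MyChart rules elsewhere.** Power/Sample Size sets a fixed sequence for message number: two messages against none, and "only if it is significant then test 2 messages vs. 1 message, thus the type I error rate of 0.05 is retained". On the cells with one tailored message (A) and two standard messages (B), it says "We assume no difference between A vs. B and thus not consider powering the comparison between these two groups". That pair is left to an exploratory non-inferiority analysis. The Analysis section repeats the non-inferiority plan but not the sequence.

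**SAP (12-17 trial only).** Sections 2.3.2 and 2.3.3 fit logistic models across the three groups. They mention neither pairwise tests nor an adjustment.

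**The concern.** The 80% describes tests that the Analysis section does not plan to report. An adjusted p value is harder to bring below 0.05 than an unadjusted one, so the size-setting contrasts must have less than the stated power unless an allowance was built in. How much less depends on the method, which is left open. The gap between a stepwise and a single-step method exceeds 20 points in Personal Contacts, enough to decide whether the comparison of one personal contact with one extra automated message is significant.

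The family is partly open too. In Personal Contacts, four groups clearly give six pairs per outcome, but the text does not say whether the adjustment also runs across the three outcomes. In MyChart it does not say which pairs count, nor how the tailored-vs-standard contrasts are controlled alongside the sequence, which covers message number only.

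**Working it through.** **Inputs (Protocol, Power/Sample Size).**
- Personal Contacts: C (one message) 20%, B (two messages) 35%, A (one message plus contact) 50%, AB (two messages plus contact) 65%.
- MyChart: no message 2%, C (one standard) 10%, B (two standard) 20%, A (one tailored) 20%, AB (two tailored) 30%.
- Televox 6-11: 2%, 20%, 30%. Televox 12-17: 2%, 30%, 40%.
- SAP sections 1 and 1.1 (12-17): at least 859 in total, with 2%, 20%, 30%; 859 / 3 ≈ 286 per arm.

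**Step 1. Reproduce the stated sizes at unadjusted two-sided 0.05.** With z = 1.960 and 0.842, (1.960 + 0.842)² = 7.849.
- Personal Contacts, A vs B, unpooled: 7.849 × (0.50×0.50 + 0.35×0.65) / 0.15² = 7.849 × 0.4775 / 0.0225 = 166.6, stated as 167. The other five contrasts also match.
- MyChart, A vs AB, pooled, mean rate 0.25: [1.960√0.375 + 0.842√0.37]² / 0.10² = 293.2, stated as 293.
- Televox, by the same formula: 293.2 for 20 vs 30% and 355.9 for 30 vs 40%, stated as 293 and 356.

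No multiplicity allowance is built in.

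**Step 2. Bonferroni by formula.** Power = Φ{[d√n − z√(2p̄q̄)] / √(p₁q₁ + p₂q₂)}, with z taken at 0.05/m two-sided.
- Personal Contacts, six pairs (z = 2.638), n = 167: (1.938 − 2.638×0.699) / 0.691 = 0.136, so 55%.
- MyChart, five listed contrasts (z = 2.576), n = 293: (1.712 − 2.576×0.612) / 0.608 = 0.22, so 59%. With ten pairs (z = 2.807): −0.01, so 49-50%.
- Televox, three pairs (z = 2.394), n = 293: (1.712 − 2.394×0.612) / 0.608 = 0.40, so 66%.

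**Step 3. Stepwise methods by simulation.** These used 60,000 simulated trials of pairwise logistic Wald tests at the hypothesised rates, within one outcome. The Monte Carlo standard error is about √(0.8×0.2/60,000) = 0.2 points. Entries are power in per cent.

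| Trial, n per group, family | Contrast | Unadjusted | Bonferroni | Holm | Hochberg |
|---|---|---|---|---|---|
| Personal Contacts, 167, six pairs | A vs B | 80 | 55 | 78 | 79 |
| Personal Contacts, 167, six pairs | A vs AB | 80 | 55 | 76 | 78 |
| MyChart, 293, five listed | A vs AB, B vs AB | 80 | 59 | 75 | 77 |
| MyChart, 293, all ten | A vs AB, B vs AB | 80 | 49 | 67 | 68 |
| Televox 6-11, 293, three pairs | two message arms | 80 | 66 | 80 | 80 |
| Televox 12-17, 356, three pairs | two message arms | 80 | 66 | 80 | 80 |
| Televox 12-17 at SAP size, 286 | two message arms | 79 | 64 | 79 | 79 |

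Tukey is close to Bonferroni: 58% and 57% in Personal Contacts.

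**Why the pattern looks like this.** In Televox both comparisons with no message are almost certain to be rejected, so Holm tests the remaining pair at the full 0.05. In Personal Contacts three pairs have power above 99%, so the other three start at 0.05/3 and the loss is small. In MyChart, A vs B has no true difference under the hypothesised rates. If it is in the family it usually stays unrejected and holds the size-setting contrasts at 0.025 or less, which costs about 7 points (75% to 67-68%).

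**Step 4. Larger enrolment.** 712 / 4 = 178 per group in Personal Contacts gives about 80% and 79% under Holm. In MyChart, Holm on the five contrasts reaches 80% at about 325 per group (5 × 325 = 1625, against 1465).

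**The case against.** The strongest reply is that little power is lost and the plan already covers it. The sizes are floors, the children already eligible for Personal Contacts exceed the target, both trials expect to exceed their targets, and a stepwise method costs only 1 to 5 points. This largely stands. It makes the Holm shortfall minor, but it does not make the 80% true at the sizes where it is claimed, and it does not supply the missing method.

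Four stronger readings are tempting, and the documents support none of them.
- *The trials are underpowered and must enrol more.* That presumes Bonferroni, which the protocol does not name, and treats the minimums as fixed. For Televox it fails outright under Holm, and the 79% at the SAP's size comes from the smaller number rather than from the adjustment.
- *The MyChart sequence and the Analysis section contradict each other.* A fixed sequence is a valid way to handle multiplicity, and Power/Sample Size states it as a commitment. What is missing is a cross-reference and a rule for the contrasts outside it.
- *MyChart's type I error is inflated because the tailored contrasts are tested at 0.05 beside the sequence.* The 0.05 there is a sizing input. The Analysis section says each comparison's p value is adjusted, so no such unadjusted test is planned.
- *The SAP withdraws the adjustment for ages 12-17.* It is silent, and the protocol's promise for that trial remains in force.

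Nor is Holm the only acceptable choice: Hochberg does slightly better here.

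**Conclusion.** The concern holds for Personal Contacts and MyChart, at modest size. Under Holm or Hochberg, the size-setting contrasts have 76-79% power in Personal Contacts and 75-77% in MyChart (five listed contrasts), not 80%. Under single-step Bonferroni they have 55% and 59%. Televox keeps its 80% at 293 and 356 per group under Holm, and drops to 64-66% (counting the SAP's size) only under Bonferroni. The main defect is therefore the unnamed method. The absent cross-reference to the MyChart sequence and the SAP's silence are secondary.

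These figures assume the hypothesised rates, equal groups at the minimum sizes, two-sided tests (inferred, because they reproduce the stated sizes) and adjustment within one outcome. Adjusting across outcomes as well would lower them. The MyChart figures are for cell-by-cell comparisons. If the sequence pools over message type, two vs one message compares 586 with 586 at 25% vs 15% and has about 99% power.

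**What to change.** - **Protocol, Analysis:** name a stepwise familywise method, such as Holm (Hochberg would also do), rather than single-step Bonferroni or Tukey. Apply it within each outcome to the six Personal Contacts pairs and to the three pairs of each Televox trial, and state whether it also spans outcomes.
- **MyChart:** refer in the Analysis section to the fixed sequence and say whether it pools over message type. State how the tailored-vs-standard contrasts are controlled alongside it. Keep A vs B outside the family as the exploratory non-inferiority comparison.
- **Power/Sample Size:** restate power for the adjusted tests at the minimum sizes (under Holm, about 76-78% for Personal Contacts and 75% for MyChart on the five listed contrasts, or the figure for the sequence chosen). Note the larger enrolment expected, and drop the full-power wording for these two trials at those sizes. The Televox sizing statement can stand under Holm.
- **SAP for ages 12-17:** cross-refer to the same rule. If it is added after the 8/5/21 study end date in section 2.2.1, mark it so, since it cannot then count as prespecified.

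The cost is wording and a slightly less favourable stated power. No extra enrolment, data or procedures are needed.

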PPC	Hi, this is [Staff First Name] from PPC. [Pt first name] is due for a check up. I'll call in a day or two to help schedule that appointment or you can walk in today to have your child seen! You can also call [contact], option 1 to schedule.	Hi, this is [First Name] from PPC. I noticed that [Child's First Name] is due for a check up. Can I schedule that for your right now? Alternate script for leaving a voice message: Hi, this is [First Name] from PPC. I noticed that [Child's First Name] is due for a check up. Sorry I missed you. Please call [contact], option 1 to schedule your appointment or walk in today to have your child seen.

*Scripts have been translated into Spanish versions by Interpreter Services

Response variables (outcomes):

- Appointment **was scheduled** within 2 weeks of intervention (Y/N) (date of actual appointment may be greater than 2 weeks from intervention)
- Appointment **was completed** within 8 weeks of intervention (Y/N). Appointment completed within 8 weeks of randomization will be used for group who does not receive any intervention.
- (Primary Outcome) Receipt of MMR by 15 months of age or receipt of 2nd MMR dose by 3 months after randomization (Y/N)
- Receipt of 1st COVID vaccination (ages 12-17 years) within 8 weeks of first intervention (Y/N)
- Family member receipt of COVID vaccination in our health system within 8 weeks of first intervention

Blocking: (controlling for factors that might influence the outcome)

- Age (12-14 months, 4 years)
- Clinic location (PPC, HPC, FPC)

Personal Contacts (12-14 months & 4-year-olds) Trial:

Randomization: Eligible patient will be identified by running a report in the electronic health record (EHR). We will run this report, stratified by clinic location, and randomly assign patients into one of the four groups created by our 2 X 2 design. Groups will receive their assigned intervention in one of four successive weeks with the sequence randomly assigned (see table below).

Replication: We will conduct a total of 3 trials, repeating the randomization procedure every 4 weeks to identify children who become eligible: Weeks 1-4 = trial #1, weeks 5-8 = trial #2, weeks 9-12 = trial #3.

Outreach Methods Study Protocol & SAP

Version 1.1, 1/14/22

	1 automated message sent	2 automated messages sent
0 personal contact attempt	Message sent on Thu (weeks 3, 5, 10)	Message sent on Thu & Fri (weeks 4, 6, 12)

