1 personal contact attempt	Above plus attempt Mon – Fri of following week (weeks 2, 7, 11)	Above plus attempt Mon – Fri of following week (weeks 1, 8, 9)

MyChart and Televox Trials (6-17 years old):

Randomization: Eligible patients will be identified by running a report in the electronic health record (EHR). We will run this report, stratified by clinic location, and randomly assign patients into one of the study groups as described above. Groups will receive their assigned intervention in one of four successive weeks with the sequence randomly assigned (see table below).

We will randomize children who are eligible and implement interventions for each trial : Weeks 1-3 = Televox Trial 12-17yo, Weeks 4-7 = Televox Trial 6-11yo, Weeks 8-10 = MyChart Trial.

MyChart Trial:

	no message	1 MyChart message sent	2 MyChart messages (e.g. Mon and Thurs)
Standard Message	No intervention	Week A	Week B
Tailored Message		Week A	Week B

Televox (6-11yo) Trial:

no message	Low Tailored Message 2 automated standard messages sent (e.g. Thu, Fri) (weeks C, C)	High Tailored Message 2 automated tailored messages sent (e.g. Thu, Fri) (weeks D, D)
-------------------	--	---

Televox (12-17yo) Trial:

no message	Low Tailored Message 2 automated tailored messages sent (e.g. Thu, Fri) (week A)	COVID Tailored Message 2 automated messages sent (e.g. Thu, Fri) (week B)
-------------------	--	---

Of note, automated messages and/or personal contact attempts will not be completed if the parent schedules an appointment after being randomized but before receiving the intervention.

Covariates for logistic regression: (factors that might influence the outcome if not balanced across groups)

1. Child age at the time of randomization (rationale: visits are less frequent for children age 4 years)
2. Parent preference for call vs. text mode of contact (rationale: calls may be more likely to get blocked than texts)
3. Parent with activated MyChart account (Y/N) (rationale: not dependent on calling scheduling center to make appointment)

4. Access to appointment: Number of days to 3rd next available appointment at patient's clinic at time their first automated message is sent
5. Patient receipt of any past immunizations (Y/N) (rationale: vaccine refusing parents will be unlikely to change even if they return for well child check)
6. School-age vs. adolescent patient age (rationale: adolescents less likely to get yearly check-ups)
7. Historical no-show rate

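### The supplementary per-protocol analysis groups families by contacts received, but a contact is withheld once the family books, so comparisons of one versus no personal attempt are distorted by an outcome

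*Combined protocol and SAP*

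**What the plan says.** The protocol's Analysis section plans intent-to-treat logistic regression for every trial and then adds: "We will also conduct per-protocol analyses according to the interventions actually received by the participants". Its own example of receipt differing from allocation is that "a parent allocated to group A might schedule an appointment after receiving the automated message and therefore would not receive a personalized contact attempt".

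The general rule stands just before the covariate list: "automated messages and/or personal contact attempts will not be completed if the parent schedules an appointment after being randomized but before receiving the intervention".

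In the Personal Contacts schedule the automated message goes out on Thursday (or Thursday and Friday). The personal-attempt arms are described as "Above plus attempt Mon – Fri of following week". The attempt therefore comes 4 days (Monday) to 8 days (Friday) after the Thursday message.

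Under Response variables, booking is an outcome, counted "within 2 weeks of intervention (Y/N) (date of actual appointment may be greater than 2 weeks from intervention"). Completed visits and MMR receipt are further outcomes.

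The per-protocol set is not otherwise defined. The text does not say whether a family with a withheld contact is moved to the group matching what it received or is left out. The appended SAP covers only the 12-17 year trial. Its section 2.3 analyses subjects as allocated, and it contains no per-protocol analysis.

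**The concern.** Read together, these rules make exposure depend on an event after randomisation that is itself an outcome and lies on the path to the visit and MMR. Write C for one message and no attempt, B for two messages and no attempt, A for one message and one attempt, and AB for two messages and one attempt. Early bookers in A and AB lose their attempt. Sorted by receipt, they leave A and AB and join C and B respectively. The contacted groups are then depleted of families who were going to act anyway, and the uncontacted groups are enriched with them.

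Covariate adjustment does not repair this. It is planned only where groups differ on the listed characteristics, and booking after the message is not one of them.

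The stake is how personal contact is read. The Power/Sample Size section says: "Because of the significant cost involved in making personal contacts, the minimal difference in outcome that would make it worth the effort is high". Potential Benefits says the results will guide how resources are allocated to outreach. A per-protocol figure that understates personal contact, or makes an ineffective contact look harmful, could be taken as evidence against the intent-to-treat result when it reflects selection only.

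**Working it through.** **The plan's own figures.** The documents give no number for the per-protocol analysis. The planned MMR rates are C 20%, B 35%, A 50%, AB 65%. With the unpooled two-proportion formula, two-sided alpha 0.05 and 80% power, n = (p1(1-p1) + p2(1-p2)) × (1.96 + 0.8416)² / (p1 - p2)². For A vs B this is (0.25 + 0.2275) × 7.849 / 0.0225 = 166.6, so 167. The other contrasts reproduce as well (36, 136, 167, 40, 16), which matches "To fully power the 2 X 2 factorial trial, we estimate needing 167 per group X 4 groups = 668 total subjects". A vs B and A vs AB set the size.

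**Assumed inputs.** The documents give neither of these:
- e = share of A and of AB that books before the attempt (taken as equal)
- q = success rate of early bookers

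Arms are of equal size, and in this model only personal attempts are withheld.

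**Direction relative to families actually contacted.** Let r be the success rate of uncontacted non-bookers and d the effect in contacted families. A and C are treated alike until the attempt, so they share e, q and r.
- Regrouped: (r + d) - [2eq + (1 - e)r]/(1 + e) = d - 2e(q - r)/(1 + e)
- Early bookers excluded from A only: d - e(q - r)

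Both fall below d whenever q exceeds r.

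**Size relative to intent-to-treat.**
- A = (0.50 - qe)/(1 - e); AB = (0.65 - qe)/(1 - e), under either handling
- Regrouped: C = (0.20 + qe)/(1 + e); B = (0.35 + qe)/(1 + e)
- Excluded: C = 0.20; B = 0.35

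At e = 10%, q = 80%: A = 0.42/0.90 = 46.7%, AB = 0.57/0.90 = 63.3%, regrouped C = 0.28/1.10 = 25.5%, regrouped B = 0.43/1.10 = 39.1%.

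| Contrast | Intent-to-treat | Regrouped | Excluded |
|---|---|---|---|
| A vs C | 30 | 21.2 | 26.7 |
| AB vs B | 30 | 24.2 | 28.3 |
| A vs B | 15 | 7.6 | 11.7 |

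**Break-even q.** Setting each contrast equal to its intent-to-treat value gives, for regrouping, q = (0.70 + 0.30e)/2 for A vs C, (0.85 + 0.15e)/2 for A vs B and (1.00 + 0.30e)/2 for AB vs B. For exclusion it is the rate of the attempt arm itself. At e = 10%:

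| Contrast | Regrouped | Excluded |
|---|---|---|
| A vs C | 36.5% | 50% |
| A vs B | 43% | 50% |
| AB vs B | 51.5% | 65% |

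Below these values the contrast is not understated relative to intent-to-treat.

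**No true effect.** With 20% in every arm, e = 5% and q = 80%, the attempt arms show 0.16/0.95 = 16.8%. The no-attempt arms show 0.24/1.05 = 22.9% regrouped or 20% excluded. The differences are -6.0 and -3.2 points.

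**How far it can go.** Regrouped A vs B is zero where 0.15 + 0.85e = 2qe. That is e = 0.15/0.75 = 20% at q = 80%, or 0.15/1.15 = 13.0% at q = 100%. A vs C stays positive: early-booker successes cannot exceed C's 20%, so its lowest value is 0.30/0.80 - 0.40/1.20 = 4.2 points.

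**Booking before the first message.** The withholding rule also covers this case, which the model above leaves out. Within the three four-week blocks the scheduled positions are C 3, 1, 2; B 4, 2, 4; A 2, 3, 3; AB 1, 4, 1. The mean block weeks are C 2.0, B 3.3, A 2.7, AB 2.0. The time in which a family can book and lose its first message therefore differs by arm.

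**The case against.** The strongest reply is that this is a secondary matter. Intent-to-treat comes first for every trial, no sample size rests on the per-protocol analysis, the protocol openly acknowledges that receipt can differ from allocation, and the SAP analyses as allocated. All of that stands. It limits the severity but does not make the by-receipt comparison sound: the protocol names the case without recognising the selection it causes or saying how to handle it.

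Several stronger readings are tempting, and the documents do not support them.

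- **That the bias always runs against personal contact.** The direction depends on the comparator. At e = 10%, q = 45%, A vs C is 0.455/0.90 - 0.245/1.10 = 28.3 points regrouped, but 50.6 - 20 = 30.6 excluded. One lies below the intent-to-treat 30 and the other above.
- **That B vs C and A vs AB are immune under the null.** This needs equal early booking and ignores the unequal waits before the first message. At the planned rates, with e = 5% in A, 10% in AB and q = 80%, B vs C becomes 39.1 - 22.9 = 16.2 and A vs AB becomes 63.3 - 48.4 = 14.9, against 15 for each.
- **That early bookers succeed by definition on the two-week scheduling outcome.** Response variables does not say which contact starts the clock when there are several. For the Personal Contacts trial, Analysis lists completed rather than scheduled appointments at two weeks.
- **That the same sizes carry over to MyChart or message content.** Analysis does list outcomes there "for each of the binary outcomes: scheduled appointment within 2 weeks", but the protocol does not say whether a second automated message is withheld after a booking prompted by the first, and it gives no scheduling rates.
- **That A vs B would plausibly vanish.** At e = 20%, q = 80%, early bookers would supply 0.16/0.20 = 80% of C's successes, leaving its other families at 0.04/0.80 = 5%. At 13% and 100% the share is 65% and the remainder is 8%. Both are extreme.

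**Conclusion.** The concern holds for the supplementary per-protocol analysis, chiefly in the Personal Contacts trial. Grouping by receipt conditions on booking, which is an outcome. Relative to the effect in contacted families, one versus no attempt is biased against personal contact if early bookers would succeed more often than uncontacted non-bookers. That is plausible, because booking is a step toward the visit. Relative to intent-to-treat, understatement requires an early-booker success rate above the break-even values.

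The size cannot be fixed from the documents. The illustrative shifts rest on assumed early-booking shares and success rates, equal early booking in A and AB, and no booking before the first message. Contrasts of one versus two messages by receipt may also be biased through the unequal waits, with size and direction not determinable from the documents.

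A reader might infer that the trial's main result is compromised. It is not: intent-to-treat and the 12-17 year SAP are unaffected. This should be corrected, but it does not threaten the primary inference.

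**What to change.** In the protocol's Analysis section, replace the by-receipt definition with adherence to the assigned strategy, stated as contact unless already booked.

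- A message or attempt withheld because the family had booked, including before the first message, counts as adherent, and the family stays in its randomised arm.
- Only true deviations leave the per-protocol set: a wrong contact sent, or an assigned contact not attempted for another reason. Report their number and reasons by arm.
- State that such exclusions fall more heavily on arms assigned more contacts (a missed personal attempt can occur only in A and AB), so the result only supports intent-to-treat. For example, if 10% of A were not attempted and those families had a 20% rate (both assumed), removing them would move A from 50.0% to (0.50 - 0.10 × 0.20)/0.90 = 53.3%.
- Label any table by receipt as descriptive.

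The cost is a few sentences and a small amount of extra reporting. The booking and contact dates are already needed for the scheduling outcome and the withholding rule. The price is a per-protocol result that will lie close to intent-to-treat and so add less separate information.
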